6.10.3. Deaths and Other Serious Adverse Events

The listing of all deaths by patient for the Enrolled Population will be provided as part of the SAE listing, regardless of the investigator's or the sponsor's judgment about causality. Each listing will include study ID, investigator ID, patient ID, treatment sequence, treatment, baseline age, sex, associated AE, first and last dose date for open label Humalog and randomized IP, and the event date.

6.10.4. Hypoglycemic Events and Other Adverse Events

The analysis plans for the following AEs are discussed in Section 6.10.4.1 through Section 6.10.4.5:

- hypoglycemic events
- systemic hypersensitivity reaction
- infusion site reaction
- hepatobiliary events
- malignant neoplasm events

These AE analyses will be similar to the TEAE analyses, refer to [Table ITSM.6.3](#) for the requirement of analysis data for a specific analysis period.

6.10.4.1. Hypoglycemic Events

Hypoglycemia events that occur during the study will be captured using a paper diary starting from Visit 2 through Visit 801. Whenever hypoglycemia is suspected, the patient should record the blood glucose value, any associated symptoms, and the treatment administered. A set of events is counted as 1 event in analysis if the duration between adjacent events is ≤ 30 minutes. The event with the highest severity will be selected for analysis. Severity will be determined in the order of: 1) whether it is a severe hypoglycemia, 2) whether it has symptoms of hypoglycemia reported, and 3) the lowest blood glucose value that occurred. If there are multiple events tied in all 3 aspects, the event with the largest number of nonmissing responses to the questions of nocturnal hypoglycemia and postmeal time frame will be selected. If there are still multiple events tied, the latest event (based on event time) will be selected.

The following types of hypoglycemia events will be derived in the analysis data sets: documented hypoglycemia, severe hypoglycemia, nocturnal hypoglycemia, probable symptomatic hypoglycemia, and overall hypoglycemia. Only severe hypoglycemia will be collected as AEs and all episodes of severe hypoglycemia will be considered as SAEs. Documented hypoglycemia (including documented symptomatic hypoglycemia, documented asymptomatic hypoglycemia, and documented unspecified hypoglycemia) will be based on $BG \leq 70$ mg/dL and $BG < 54$ mg/dL.

[Table ITSM.6.4](#) provides detailed statistical methods for each endpoint related to hypoglycemia. For these analyses, hypoglycemia events from first dose to last dose of IP will be summarized. Additional analyses for other types of hypoglycemic events not mentioned in the table may be conducted as needed.

A listing of patients with at least 1 severe hypoglycemia reported (as SAE) after randomization (including Visit 801) will be provided.

A list of MedDRA PTs will be used for the narrow search of potential severe hypoglycemia in spontaneously reported AEs. The events identified through the search strategy that are also reported as SAEs will be summarized and compared between treatments. Prescott's exact test will be used to assess the treatment difference in the proportion of patients with potential severe hypoglycemia.

Table ITSM.6.4. Summary of Analyses for Endpoints Related to Hypoglycemia

Endpoint	Analysis Period^a	Statistical Method
Rate of hypoglycemic events (per patient per year) 
 All Documented^b Nocturnal^b Non-Nocturnal (or Daytime) (Documented and between waking and bedtime)^b 	0-2, 0-4, 2-4 weeks	Wilcoxon signed-rank test
Incidence of hypoglycemic events 
 All Documented^b Nocturnal^b Non-Nocturnal (or Daytime)(Documented and between waking and bedtime)^b 	0-2, 0-4, 2-4 weeks	If there are ≥ 5 patients with at least one event within the specified time period, a generalized linear mixed model with options of the binomial distribution and logit link function with treatment, period, sequence. The within-patient error will be modeled as a compound symmetry without heterogeneous variance-covariance matrix. If the model does not converge or is not conducted due to the lower occurrence of events, Prescott's exact test will be used for analyses.
Endpoint	Analysis Period^a	Statistical Method
Rate of post-meal hypoglycemic events (per patient per year) 
 Documented^b 	$\leq 1, \leq 2, \leq 4, > 4$ and > 2 to ≤ 4 hours after start of a meal within 0-2, 0-4, and 2-4 weeks	Wilcoxon signed-rank test
Incidence of post-meal hypoglycemic events 
 Documented^b 	$\leq 1, \leq 2, \leq 4, > 4$ and > 2 to ≤ 4 hours after start of a meal within 0-2, 0-4, and 2-4 weeks	If there are ≥ 5 patients with at least one event within the specified time period, a generalized linear mixed model with options of the binomial distribution and logit link function with treatment, period, sequence. The within-patient error will be modeled as a compound symmetry without heterogeneous variance-covariance matrix. If the model does not converge or is not conducted due to the lower occurrence of events, Prescott's exact test will be used for analyses.
Rate of severe hypoglycemic events (per patient per year / 100 years)	0-2, 0-4, 2-4 weeks	Exposure adjusted rate per year / 100 years (calculated for each patient by total number of events divided by total exposure) will be provided and Wilcoxon signed-rank test will be used for treatment comparison.
Incidence of severe hypoglycemic events	0-2, 0-4, 2-4 weeks	Proportion of patients with severe hypoglycemia will be reported. The treatment comparison will be based on Prescott's exact test.

^a Treatment comparisons for severe hypoglycemia will be based upon the data collected for 0-4 weeks of each treatment period. Treatment comparisons for other categories of hypoglycemia will be only based upon the data collected for 2 to 4 weeks.

^b Hypoglycemia will be based on the thresholds of blood glucose ≤ 70 mg/dL and blood glucose < 54 mg/dL.

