9.4. Safety

9.4.1. Hypoglycemia

Patients are encouraged to perform SMBG whenever hypoglycemia may be suspected, either by symptoms experienced, CGM reading or perceived increased risk as related to dietary intake, physical activity, inadvertent or atypical insulin dosing or when prompted by pump alerts. All patients will be instructed to consider a BG ≤ 70 mg/dL to be hypoglycemia and treat appropriately.

If a hypoglycemic event is suspected, the patient should record the BG value, any associated symptoms, and the treatment administered in the study diary. The patient should contact the site as necessary. All hypoglycemia events (severe and nonsevere) must be reported on the hypoglycemia eCRF. All episodes of severe hypoglycemia must be reported as SAEs on the AE eCRF page and on the SAE eCRF page. Episodes of hypoglycemia not meeting the criteria for severe hypoglycemia should not be reported as an AE.

Hypoglycemia will be described using the following definitions:

- **Documented Glucose Alert (Level 1); BG ≤ 70 mg/dL:**
 - **Documented symptomatic hypoglycemia:** an event with typical symptoms of hypoglycemia.
 - **Documented asymptomatic hypoglycemia:** an event without typical symptoms of hypoglycemia.
 - **Documented unspecified hypoglycemia:** with no information about symptoms of hypoglycemia available (this has also been called unclassifiable hypoglycemia).
- **Documented Clinically Significant Hypoglycemia (Level 2) with similar criterion as above except for threshold BG < 54 mg/dL**
 - **Documented symptomatic hypoglycemia**
 - **Documented asymptomatic hypoglycemia**
 - **Documented unspecified hypoglycemia**
- **Severe Hypoglycemia (Level 3):** during these episodes, patients have an altered mental status and cannot assist in their own care, may be semiconscious or unconscious, or experience coma with or without seizures, and the event requiring assistance of another person to actively administer carbohydrate, glucagon, or other resuscitative actions. Blood glucose measurements may not be available during such an event, but neurological

recovery attributable to the restoration of BG concentration to normal is considered sufficient evidence that the event was induced by a low BG concentration (BG \leq 70 mg/dL [3.9 mmol/L]).

- **Other Hypoglycemia**
 - **Nocturnal Hypoglycemia:** any documented hypoglycemic event (including severe hypoglycemia) that occurs between bedtime and waking.

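### Ranking reported symptoms above lowest BG within a 30-minute diary cluster can leave a recorded low uncounted as documented hypoglycemia

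*SAP*

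**What the plan says.** SAP 6.10.4.1 counts diary events no more than 30 minutes apart as a single event. It then states: "The event with the highest severity will be selected for analysis". Severity is judged in a fixed sequence: "1) whether it is a severe hypoglycemia, 2) whether it has symptoms of hypoglycemia reported, and 3) the lowest blood glucose value that occurred". Further tie-breaks follow, but they are opened only by the condition "If there are multiple events tied in all 3 aspects".

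The same section defines documented hypoglycemia at BG ≤70 and BG <54 mg/dL, "including documented symptomatic hypoglycemia, documented asymptomatic hypoglycemia, and documented unspecified hypoglycemia". Table ITSM.6.4 applies both cut-offs to the documented, nocturnal, daytime and post-meal rows. Its footnote b begins "Hypoglycemia will be based on the thresholds of blood glucose" and gives the two values; one of the rows is "Rate of post-meal hypoglycemic events (per patient per year)". Footnote a fixes the comparison window: "Treatment comparisons for other categories of hypoglycemia will be only based upon the data collected for 2 to 4 weeks".

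Protocol 9.4.1 defines the lower tier as "Documented Clinically Significant Hypoglycemia (Level 2) with similar criterion as above except for threshold BG" <54 mg/dL, with symptomatic, asymptomatic and unspecified subtypes. It keeps probable symptomatic hypoglycemia for symptoms with no BG reported.

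Neither document says that a cluster's lowest BG is carried to the record that is kept, or that selection is run separately for each threshold.

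**The concern.** The protocol grades non-severe events by BG, and symptoms are a subtype within each grade. The SAP's selection order puts the subtype ahead of the grade. One record is kept and then tested against ≤70 and <54, so a low that the patient measured and wrote down can disappear from the count because another record in the cluster carried symptoms.

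What is at stake is the diary-based count for secondary endpoint 6, which names no threshold and which the SAP analyzes at both. The nocturnal, daytime and post-meal rows draw on the same selected records. The wording also leaves room for two programmers to derive different counts, since one might apply the order literally and the other within each threshold.

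**Working it through.** The plan gives no figure to reproduce. The check is to apply the rule as written to every possible pair of records.

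**Inputs (SAP 6.10.4.1, Protocol 9.4.1).** A non-severe diary record is one of 7 types: BG <54 with symptoms yes, no or unknown; BG 54-70 with symptoms yes, no or unknown; or symptoms with no BG. Two reading assumptions are needed. Symptoms no and unknown rank equally, because the criterion is whether symptoms were reported. A missing BG ranks below any recorded BG when symptom status ties.

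**Number of patterns.**
- Unordered pairs: 7 × 8 / 2 = 28.
- Pairs with no BG <54: 4 × 5 / 2 = 10, so 28 − 10 = 18 contain a BG <54.
- Only one pair (both without BG) has no BG ≤70, so 27 contain one.

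**Patterns that lose a label under the literal order** (non-symptomatic means no or unknown, hence 2 types per row):

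| Records in the cluster | Record kept | Counted at <54? | Counted at ≤70? | Types |
|---|---|---|---|---|
| <54 non-symptomatic + 54-70 symptomatic | 54-70 | lost | yes | 2 |
| <54 non-symptomatic + symptoms, no BG | no BG | lost | lost | 2 |
| 54-70 non-symptomatic + symptoms, no BG | no BG | not applicable | lost | 2 |

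- At <54: 2 + 2 = 4 lost, so 18 − 4 = 14 of 18 are counted.
- At ≤70: 2 + 2 = 4 lost, so 27 − 4 = 23 of 27 are counted.
- Distinct patterns affected: 6. None gains a label, so the error runs one way.

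Example for the first row: 48 mg/dL without symptoms and 65 mg/dL with symptoms. Neither is severe, symptoms decide, and the 65 record is kept. The cluster counts at ≤70 and not at <54. Example for the second row: 50 mg/dL without symptoms and a symptomatic entry without BG. The entry without BG is kept and the cluster becomes probable symptomatic, although a BG was recorded within it.

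These are counts of logical patterns, not expected frequencies.

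**Size.** In a 14-day window, one event is worth 365.25 / 14 = 26.1 events per patient-year for that patient, or 26.1 / 36 = 0.72 on the mean of 36 completers. Any single event carries that weight; it does not say how many are lost.

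The documents give no data on repeat records or symptom reporting, so only an illustration is possible. Every input here is an assumption: first BG uniform on 42-70 mg/dL; second BG higher by a mean of 8 (SD 8), with second records above 70 dropped; symptoms on 50-80% of records. The share of <54 clusters not counted at <54 is then:
- 0.20-0.60% if 10% of clusters have a second record and the two symptom reports correlate 0.8-0.95;
- 0.41-2.94% if 20-50% have one, at the same correlations;
- up to 7.20% if 50% have one and the reports are independent.

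Keeping second records above 70 changes the range at correlation 0.8 and a 20-50% second-record share from 0.84-2.94% to 0.91-3.22%. None of these figures is an estimate or a bound.

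**Effect on the comparison.** If a share q is lost under both treatments, the rate ratio is unchanged and the rate difference is multiplied by (1 − q).

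**The case against.** The strongest case is that this is a prespecified choice of which diary entry represents a cluster, applied identically to two blinded treatments, with no changed conclusion in sight. Most of that stands. The loss needs a second record within 30 minutes and a particular mix of symptoms and BG. The pattern with a missing BG is less likely still, because patients are told to record the BG value for each suspected event and must be willing to confirm hypoglycemia with the meter (Protocol 6.1, criterion 12). Sensor time <54 mg/dL is a separate secondary endpoint, and CGM episodes <54 are also analyzed. Neither uses this rule, which limits the consequence but does not repair the diary count.

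Three stronger readings are tempting, and the documents do not support them. A reader might infer that the SAP contradicts Protocol 9.4.1. It does not: the protocol has no rule for merging records, so the order fits poorly with its grading but breaks no stated rule. A reader might infer that the rule favors one insulin. Nothing in either document suggests that the losing patterns would be more common under one treatment. A reader might infer a material undercount. The percentages above rest wholly on assumed inputs and cannot establish one.

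What does not fall away is that the rule as written gives a lower count than the diary supports, at thresholds the SAP itself uses.

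**Conclusion.** The point holds at low severity. As worded, SAP 6.10.4.1 can drop a recorded low from the <54 count, or from both documented counts when the kept record has no BG. The error is an undercount only, confined to diary-based documented hypoglycemia: secondary endpoint 6 and the nocturnal, daytime and post-meal rows of Table ITSM.6.4. Its frequency cannot be computed from the documents and is probably small. No directional treatment bias is shown. The primary endpoint, CGM outcomes and severe hypoglycemia counts are unaffected.

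The conclusion rests on reading the order as strictly sequential, which the condition for the later tie-breaks supports, and on the absence of any statement that selection is per threshold. If per-threshold selection was intended, the loss at both thresholds disappears once the text says so.

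**What to change.** Amend SAP 6.10.4.1 as follows:
- Form the 30-minute clusters once, from all records. Keep one event per cluster and keep severe status first.
- For each threshold (≤70 and <54), apply the existing severity order and tie-breaks only among the cluster's records that meet that threshold. Any cluster with a qualifying record is then counted there.
- Classify a cluster as probable symptomatic only if no record in it is documented.

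In the enumeration this counts 18 of 18 patterns at <54 and 27 of 27 at ≤70. Each label comes from a record that the patient actually made, with no mixing of the symptoms of one entry with the BG of another.

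The cost is one or two sentences and slightly more programming, on data already collected; the number of clusters does not change. The downside is that a cluster's symptom, nocturnal or post-meal label may differ between the two thresholds. The symptom subtype differs in 2 of the 28 patterns (the first row of the table). In 4 patterns (the first two rows) the symptomatic record is not used at <54. A footnote to Table ITSM.6.4 should say so.

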6.10.4.2. Systemic Hypersensitivity Reaction

The number and proportion of patients experiencing treatment-emergent potential systemic hypersensitivity reactions will be summarized and compared by treatment using Prescott's exact test. The following Standardised MedDRA Query (SMQ) will be used to identify potential systemic hypersensitivity reactions from all TEAEs:

- anaphylactic reaction (SMQ). Besides using the narrow and broad terms designated within the SMQ, the following search algorithm will also be implemented as another approach to determine if a patient had an anaphylactic reaction: if a patient (had at least 1 event in Category A) or (had at least 1 event that is in category B and also had at least 1 event that is in category C) or (had at least 1 event that is in category D and [also had at least 1 event in category B or at least 1 event in category C])
- angioedema (SMQ)
- hypersensitivity (SMQ)

Specifically, the following need to be performed: (1) any narrow or algorithmic term from any 1 of the 3 SMQs indicated above (that is, combined search across narrow and algorithmic portions of all 3 SMQs); (2) any narrow scope term within each SMQ, separately (that is, narrow SMQ search); (3) any term within each SMQ, separately (that is, broad SMQ search); (4) narrow scope term search within each SMQ, report the PT nested within each SMQ.

A similar summary will be provided for the TEAE reported by the investigator as possibly related to study drug.

Note that an individual patient may contribute multiple events. Also, a single event may satisfy multiple SMQs, in which case the event contributes to every applicable SMQ.

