observed from all associated LLTs mapping to the MedDRA PT during the corresponding randomized treatment period for the specified treatment. No statistical comparison between treatments will be conducted.

The number and percentage of patients who experienced a SAE including deaths and SAEs temporally associated or preceding deaths will be summarized by treatment using MedDRA PT (without regard to SOC). Events will be ordered by decreasing frequency within SOC. A listing of all SAEs (including data collected during the safety follow-up period) will also be provided.

The number and percentage of patients who discontinued from study in Period I and Period II due to an AE will be summarized by treatment using MedDRA PT (without regard to SOC). Events will be ordered by decreasing frequency. A listing of all AEs as reason for study discontinuation will also be provided.

For events that are gender-specific (as defined by MedDRA), the denominator and computation of the percentage will include only patients from the given gender.

Table ITSM.6.3 summarizes the planned analyses and the requirement of analysis data for different analysis periods.

Table ITSM.6.3. Adverse Event Analysis Periods

Analysis Period	Analysis Population	Analysis	IP USE	Treatment
Lead-in Period	Enrolled Population	AE overview; TEAE by PT; SAE, discontinuation due to AE	N/A	Open-label Humalog
Treatment Period (0-8 Weeks)	Randomized Population	AE overview; TEAE by PT nested within SOC and by PT; TEAEs by maximum severity; SAE; discontinuation due to AE; other notable AEs	All data regardless of IP use	LY900014, Humalog
Safety Follow-up Period	All patients in the Randomized Population who enter follow-up period	TEAE by PT	All data	Overall ^a

Abbreviations: AE = adverse event; IP = investigational product; N/A = not applicable/available; PT = preferred term; SAE = serious adverse event; SOC = system organ class; TEAE = treatment-emergent adverse event.

^a overall means that data will be summarized in total and no by-treatment summary or statistical analysis will be included.

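### The anaphylaxis algorithm in SAP 6.10.4.2 pairs events in the same patient without any closeness-in-time condition, so unrelated events up to 4 weeks apart can be flagged as a potential reaction

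*SAP*

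**What the plan says.** SAP 6.10.4.2 uses three standardised MedDRA queries, which "will be used to identify potential systemic hypersensitivity reactions from all TEAEs". For the anaphylactic reaction query it adds a second route: "the following search algorithm will also be implemented as another approach to determine if a patient had an anaphylactic reaction". A category A event is enough alone. Otherwise the patient qualifies with a pair: either the patient "had at least 1 event that is in category B and also had at least 1 event that is in category C", or a category D event is accompanied by one from B or C. The unit is the patient, and no condition links the dates of the two events.

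The result "will be summarized and compared by treatment using Prescott's exact test". Of the four outputs the section requires, the algorithm is named in the first, which combines narrow terms and algorithmic hits across all three queries.

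SAP 6.10.4 adds "These AE analyses will be similar to the TEAE analyses" and refers to Table ITSM.6.3. The randomized row there is labelled "Treatment Period (0-8 Weeks)" and names LY900014 and Humalog in its treatment column.

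**The concern.** The algorithm infers one reaction from two component events, which makes sense only if they belong to the same episode. Without an onset condition, a category B event in week 1 and an unrelated category C event in week 4 meet the rule in full. A programmer would have no reason to add a window, because the rule is complete as written.

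The SAP does write such conditions elsewhere. Section 6.10.4.1 merges hypoglycemia records no more than 30 minutes apart. Section 6.10.2 confines maximum severity to the randomized period of the treatment concerned. The anaphylaxis rule has neither kind of condition.

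The stake is interpretive. In a trial of about 42 randomized patients, a single patient flagged for anaphylaxis on a new formulation would be conspicuous. Deciding after unblinding whether that flag is genuine invites a data-driven judgement.

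**Working it through.** The plan states no figure on this point, so there is none to reproduce. The check has a textual part and an illustration.

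**Text.** These places were compared for a time or period condition:

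- SAP 6.10.4.2: no window and no same-period condition for the pairs.
- SAP 6.1: adverse event analyses use each treatment's whole 4-week period.
- Table ITSM.6.2: the post-baseline window for treatment-emergent events is each 4-week randomized period.
- SAP 6.10.2: an event on a first-dose day is assigned to one period's treatment.
- Table ITSM.6.3: results are shown by treatment.

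The last four favour applying the algorithm within a treatment period. None limits the gap between paired events inside that period.

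**How far apart unrelated pairs lie.** For two independent onsets spread uniformly over 28 days, the chance of being more than w days apart is (1 − w/28)².

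- w = 1: (27/28)² = 0.93
- w = 7: (21/28)² = 0.56
- w = 14: (14/28)² = 0.25

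The share within 1 day is therefore 1 − 0.930 = 0.070 in continuous time. Counting calendar days instead gives (28 + 2 × 27)/28² = 82/784 = 0.105.

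**Expected chance flags.** Let p be the share of patients with at least one category B event in 4 weeks, and assume the same share, independently, for category C. The chance that a patient is flagged in at least one of two periods by same-period pairing is 1 − (1 − p²)². Multiply by 42, the planned number randomized, taking all to complete both periods.

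| p (assumed) | Per patient | Expected of 42 | Same, within 1 day (× 0.070 to × 0.105) |
|---|---|---|---|
| 1% | 0.0002 | 0.008 | 0.0006 to 0.0009 |
| 2% | 0.0008 | 0.034 | 0.002 to 0.004 |
| 5% | 0.0050 | 0.21 | 0.015 to 0.022 |
| 10% | 0.0199 | 0.84 | 0.059 to 0.087 |

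At p = 5%, the chance of at least one false flag is 1 − (1 − 0.0050)^42 = 19%.

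The table covers B-with-C pairs only; pairs involving category D would add to it. The SAP does not list the terms in each category and gives no rates, so p cannot be narrowed from the documents.

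**The case against.** The strongest reply is that this is meant to be a wide net. The section speaks of potential reactions, the algorithm sits beside the narrow and broad searches, and a parallel summary covers events the investigator judged possibly related to study drug. A chance pair adds at most one patient to one combined row. If it were the only case, SAP 6.1 says no Prescott p-value is produced when all events fall in one sequence, so it would not be tested. Onset dates can be checked for any flag. A window would also cost sensitivity, and no passage supports 1 day in particular. All of this stands and keeps the severity low. It does not supply the missing condition.

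A reader might go further and infer that a category B event on one insulin and a category C event on the other count together as a reaction, since the rule is at patient level and the row in Table ITSM.6.3 spans 8 weeks. Pairing over 8 weeks would roughly double the chance flags: at p = 5%, 42 × (1 − 0.95²)² = 0.40 against 0.21. The documents do not support that reading. Results are reported by treatment, the event windows in SAP 6.1 and Table ITSM.6.2 are per 4-week period, and SAP 6.10.2 ties events to a period. What remains is that the exclusion of split pairs is implied and not written.

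**Conclusion.** The missing onset condition is real under every reading of the SAP. The missing same-period statement is a smaller gap that the surrounding rules largely fill.

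The effect is small: well under one expected chance flag among 42 patients for p of 5% or less, and close to one only near 10%. These figures rest on assumed rates, independence of the two event types, uniform onset times and full completion of both periods. They show scale and do not predict what the trial will find.

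Only one safety row of potential reactions is touched. This is a cheap improvement of low severity.

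**What to change.** Add one sentence to SAP 6.10.4.2. The B, C and D combinations count only when the paired treatment-emergent events are assigned to the same treatment period and their onsets fall within a short window fixed before unblinding, for example 1 day. The reaction is credited to that period's insulin. All other qualifying pairs, including any that straddle the crossover, go into a listing with onset dates for medical review. Category A and the narrow and broad searches stay as they are.

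The 1-day length is a proposal; another prespecified window would serve. If the sponsor prefers no window, saying so and listing onset dates for every algorithmic flag would at least make the row interpretable.

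The cost is that sentence, one date condition in the program and one listing. The downside is that a true reaction whose component dates were recorded outside the window appears only in the listing, so the listing needs to be reviewed.
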